#### 2.3.4 Subgroup analyses for primary endpoints

For the primary estimand, subgroup analyses will be done for the factors listed and categorised as in Table 2–4. For baseline weight, categories based on quartiles will be used. The subgroup analyses will be done separately for each of these by including interaction term(s) with randomised treatment arm in the respective models (ANCOVA or logistic regression).

Statistical Analysis Plan		Date:	07 July 2018	Novo Nordisk
Trial ID: NN8022-4274	CONFIDENTIAL	Version:	1.0	
UTN: U1111-1177-5059	CONFIDENTIAL	Status:	Final	
EudraCT No.: 2015-005592-24		Page:	15 of 24	

### Figure 2–1 Illustration of imputation approaches for the effectiveness estimand

Jump to refere	nce (multiple imputation)
Liraglutide	AT+AD 7 MT+MD
Placebo	AT+AD MT+MD
McEvoy (multip	ole imputation)
Liraglutide	$ \begin{array}{c} AT \\ AD \end{array} \longrightarrow \begin{array}{c} MT \\ MD \end{array} $
Placebo	$ \begin{array}{c} AT \\ \hline AD \end{array} \longrightarrow \begin{array}{c} MT \\ \hline MD \end{array} $
McEvoy is done by	timing (e.g. monthly) of randomised treatment discontinuation
Sacks (single in	iputation)
Liraglutide	ATLAO $\rightarrow$ MTADLAO + 0.3 $\rightarrow$ MD
Placebo	$ \begin{array}{ c c c c c c c c c c c c c c c c c c c$
LAO: Last available	observation irrespective of whether on randomised treatment or not
An arrow indicates $AT = A$ MT = M AD = A MD = M	from which group an imputation is done vailable on randomised treatment lissing on randomised treatment vailable drop-out lissing drop-out

Statistical Analysis Plan Trial ID: NN8022-4274 UTN: U1111-1177-5059 EvdreCT No.: 2015 005502 24	CONFIDENTIAL	Date: Version: Status:	07 July 2018 1.0 Final	Novo Nordisk
EudraCT No.: 2015-005592-24		Page:	16 of 24	

Approach	Description	Assumptions
Jump to reference (multiple imputation)	Liraglutide and placebo MT+MD imputed from placebo AT+AD (i.e., all available placebo assessments at week 56)	
 
Liraglutide MD lose any treatment effect instantly after drop-out
 
Placebo AT and placebo AD are assumed to have the same weight loss
 

McEvoy (multiple imputation)	Separately for the two randomised treatment arms: MD imputed from AD by matching on time (month) of drop-out MT imputed from AT	
 
AD is representative of the MD for each randomised treatment arm
 
AT is representative of the MT for each randomised treatment arm
 

Weighted ANCOVA (wANCOVA)	No imputation. Separately for the two randomised treatment arms: AD subjects are up-weighted relative to their proportion of AD+MD and timing of drop- out AT subjects are up-weighted relative to their proportion of AT+MT	
 
AD is representative of the MD for each randomised treatment arm
 
AT is representative of the MT for each randomised treatment arm
 

Sacks (single imputation)	Liraglutide MD imputed by minimum of LAO+0.3 kg and baseline value for each month from drop-out to week 56 and either a) Placebo MD imputed by minimum of LAO+0.3 kg and baseline value for each month from drop-out to week 56 or b) MT (both randomised treatment arms) and placebo MD are imputed by LAO	

a) Liraglutide and placebo MD lose any treatment effect linearly after drop-out.

b) Only liraglutide MD lose any treatment effect linearly after drop-out. No change in treatment effect since LAO for others.

Tipping point (single imputation)	Liraglutide MD imputed by minimum of LAO+X kg (X in steps of 0.1) and baseline value for each month from drop-out to week 56. MT (both randomised treatment arms) and placebo MD are imputed by LAO	Only liraglutide MD lose any treatment effect linearly after drop-out. No change in treatment effect since LAO for others

AT available on randomised treatment, MT missing on randomised treatment, AD available drop-out, MD missing drop-out, LAO last available observation, LAO-OT last available observation on randomised treatment.

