#### Table 2–1Taxonomy of week 56 assessments being available or missing

Assessment at week 56	On drug at week 56	Type description	Type Abbreviation
Available	Yes	Available on randomised treatment: Subjects who did not discontinue randomised treatment prematurely. Include those that stop and restart trial product.	AT
	No	Available drop-outs: Subjects who discontinued randomised treatment prematurely but returned to have an assessment at week 56; so-called retrieved drop-outs.	AD
Missing	Yes	Missing on randomised treatment : Subjects who did not discontinue randomised treatment prematurely. Include those that stop and restart trial product.	МТ
	No	Missing drop-outs : Subjects who discontinued randomised treatment prematurely and did not return to have an assessment at week 56; so-called non-retrieved drop-outs.	MD

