- A single imputation approach as done by Sacks. Missing weight measurement at week 56 for subjects who drop-out (type MD) are imputed using a weight regain rate of 0.3 kg/month after last available observation (LAO) of body weight. Change from baseline is truncated whenever the extrapolation would lead to a positive weight gain relative to baseline. LAO does not need to be the same as LAO-OT as subjects are allowed to come to scheduled visits after discontinuing randomised treatment. When a subject's LAO represents a gain in weight relative to baseline, no additional gain will be imputed, and the unfavourable gain is carried forward to week 56. Missing weight measurement at week 56 for subjects on treatment (type MT) will be imputed using the LAO. The weight regain imputation will be done for both randomised treatment arms.

Statistical Analysis Plan Trial ID: NN8022-4274 UTN: U1111-1177-5059 EudraCT No.: 2015-005592-24	CONFIDENTIAL	Date: Version: Status: Page:	07 July 2018 1.0 Final 14 of 24	Novo Nordisk
UTN: U1111-1177-5059 EudraCT No.: 2015-005592-24	CONFIDENTIAL	Status: Page:	Final 14 of 24	

Additionally, a version where only the liraglutide 3.0 mg arm uses the regain rate while the placebo arm uses LAO (corresponding to a weight regain rate of 0 kg/month) will be performed.

• Tipping point analysis. In a similar manner as above for a range of weight regain rates (starting from 0.1 kg/month and in intervals of 0.1 kg/month) for MD in liraglutide 3.0 mg arm will be used to define a tipping point in which superiority of liraglutide 3.0 mg disappears. In this analysis, the placebo arm will be imputed by LAO.

Figure 2–1 and Table 2–5 give an overview of the handling of missing values at week 56 assessments.

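### SAP Table 2–5 counts weight regain from stopping drug but adds it to a last observation that may be later, contrary to SAP 2.3.2.2

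*SAP*

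**What the plan says.** **Text.** In SAP 2.3.2.2 (sensitivity analyses of the primary endpoints), MD weights are "imputed using a weight regain rate of 0.3 kg/month after last available observation (LAO) of body weight". The same paragraph notes that "LAO does not need to be the same as LAO-OT as subjects are allowed to come to scheduled visits after discontinuing randomised treatment". It truncates extrapolated regain at baseline and carries an LAO that is already above baseline forward unchanged. The tipping point is run "In a similar manner as above for a range of weight regain rates", so it inherits the LAO as its start.

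**Table.** SAP Table 2–5 has "Liraglutide MD imputed by minimum of LAO+0.3 kg and baseline value for each month from drop-out to week 56" in the regain row, with a parallel rule for placebo in part (a). The tipping-point row has "Liraglutide MD imputed by minimum of LAO+X kg (X in steps of 0.1) and baseline value for each month from drop-out to week 56".

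**Meaning of drop-out.** SAP Table 2–1 defines missing drop-outs as "Subjects who discontinued randomised treatment prematurely and did not return to have an assessment at week 56". The retrieved-drop-out multiple-imputation row of Table 2–5 reads "MD imputed from AD by matching on time (month) of drop-out", and Figure 2–1 describes that matching time as discontinuation of randomised treatment. Figure 2–1 also defines the LAO as irrespective of treatment.

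Protocol 17.3.2.2 and Table 17–5 carry the same text and the same rows. SAP 3.1 lists no change here, so neither rule is marked as replacing the other.

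**The concern.** The table's starting weight and its clock belong to different dates. The weight is the LAO, which already reflects whatever happened up to the last visit. The clock starts when the subject stopped drug. Protocol 8.1 asks subjects who stop drug to keep attending, and protocol 8.3.1 has weight measured at all visits, so an MD subject with off-drug weights is an expected case.

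For such a subject the table adds projected regain over months in which the true weight is known. If weight rose in that gap, the rise is counted twice. If it was stable or fell, regain is charged for months observed without it.

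Two programmers, one following the text and one the table, would produce different imputed weights. A tipping point in kg per month can be interpreted only if the months are defined in one way.

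**Working it through.** **1. The assumptions reused below.** The plan gives no figure for this rule. Its sample-size inputs (−9 vs −4, SD 7, 30% discontinuation, 141 per arm) give a liraglutide mean of 0.7×(−9) + 0.3×(−4) = −7.5, an SD of √(49 + 0.7×0.3×25) = 7.37, a difference of −3.5 and a Satterthwaite power of 98.28%. The SAP states 98.3%.

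**2. The two rules.** Let T be week 56, r the monthly rate, and B the baseline weight.
- Text: min(LAO + r×(T − time of LAO), B)
- Table: min(LAO + r×(T − time of stopping drug), B)

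Below the cap, table minus text = r×(time of LAO − time of stopping drug). At 0.3 kg/month, gaps of 1, 3, 6 and 9 months give 0.3, 0.9, 1.8 and 2.7 kg. The rules agree when the LAO is the weight at stopping.

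**3. Two illustrative subjects, baseline 100 kg (assumed values; 56 weeks = 12.88 months).**

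| | Stops drug | LAO | Text | Table |
|---|---|---|---|---|
| A | month 3, 92.0 kg | month 6, 92.9 kg | 92.9 + 0.3×6.88 = 94.96 kg (−5.04%) | 92.9 + 0.3×9.88 = 95.86 kg (−4.14%) |
| B | week 12 | week 40, 93.5 kg | 93.5 + 0.3×3.7 = 94.6 kg (−5.4%) | 93.5 + 0.3×10.1 = 96.5 kg (−3.5%) |

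Each is a 5% responder under the text and a non-responder under the table. For A, projecting from the weight at stopping gives 92.0 + 0.3×9.88 = 94.96 kg, the same as the text. A clock that starts at stopping is therefore coherent with the weight at stopping, but not with a later LAO. The table's extra 0.9 kg is the observed regain added again. For B no weight at stopping is given, so the example shows only the longer clock.

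**4. Shift in an arm's mean at 0.3 kg/month, cap ignored.** Assume that drug is stopped uniformly over weeks 2–54 (mean week 28), that subjects who keep attending have a last weight uniform between stopping and week 54, that 30% of the arm is MD, and that mean weight is 105 kg. The mean gap among attenders is (54 − 28)/2 = 13 weeks = 2.99 months.

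| MD subjects who keep attending | Mean gap per MD subject (months) | Excess per MD subject (kg) | Shift in arm mean (excess × 0.30/105) |
|---|---|---|---|
| 25% | 0.75 | 0.22 | 0.06 points |
| 50% | 1.50 | 0.45 | 0.13 points |
| 100% | 2.99 | 0.90 | 0.26 points |

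**5. Tipping point.** Before the cap, the table's added regain is (T − stop)/(T − LAO) times the text's at any X; for subject A, 9.88/6.88 = 1.44 times. The cap limits what this can do to % weight change. In the limit every liraglutide MD subject sits at baseline:
- Liraglutide mean: 0.7×(−9) + 0.3×0 = −6.3; variance 0.7×49 + 0.7×0.3×81 = 51.3.
- Placebo mean: −4.0 if LAOs show the full effect. If loss is linear to week 30, the average fraction reached at stopping is (28/52)×(16/30) + 24/52 = 0.75, so the placebo mean is 0.7×(−4) + 0.3×(−3.0) = −3.7.
- SE = √((51.3 + 49)/141) = 0.84. The difference is −2.3 to −2.6, z is 2.7 to 3.1, and superiority survives in roughly 78% to 87% of trials even at that limit.

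Simulation with the cap agrees: 84% to 96% of trials never tip under either rule, and the rules give different answers in about 10% to 15%. For 5% responders, with the cap and an unadjusted two-proportion test, superiority tipped below 6 kg/month in 52–55% of trials under the table and 38–51% under the text. Where both tipped, the medians were 1.5–2.0 and 2.2–3.0 kg/month.

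**6. LAO above baseline.** With an LAO of 102 kg and a baseline of 100 kg, the table's minimum gives 100 kg; the text carries 102 kg forward. This second mismatch in the same cells lowers the imputed weight, so it acts in the opposite direction.

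**The case against.** **The table is only an overview.** SAP 2.3.2.2 calls it that, and the text is a complete rule. This makes the text the natural rule to keep. It does not remove the conflict, because no passage gives the text precedence and the table cells read as formulae.

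**Drop-out might mean leaving the trial at the last visit.** The two rules would then coincide. Table 2–1 and Figure 2–1 do not use the word that way.

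**The effect is small and cautious.** This largely stands. The shift at 0.3 kg/month is a fraction of a point. In the liraglutide-only version and the tipping point the longer clock acts against liraglutide, so it cannot create false superiority. In the version with regain in both arms it partly cancels, and the net direction is unknown. Treating all of the 30% who discontinue as missing at week 56 is the plan's own sample-size simplification and an upper bound.

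**Stronger readings that a reader might infer.** Leaving out the baseline cap, simulated tipping rates for % weight change are about 1.5–1.6 kg/month (table) against 1.7–3.0 (text), which suggests a large understatement. The same table cell and SAP 2.3.2.2 both impose the cap, so this does not describe the planned analysis. Nor does the discrepancy simply grow with better retention: a subject who returns at week 56 becomes a retrieved drop-out and is not imputed.

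**Conclusion.** The text and the table give different week-56 weights for every MD subject who was weighed after stopping drug and is below the baseline cap. The table's version is wrong as written, because it pairs a later weight with an earlier clock. It is a literal double count only where regain occurred between stopping drug and the LAO.

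The excess of 0.3 kg (or X kg) per month of gap is exact below the cap. The 0.06 to 0.26 point shift rests on the assumed stop times, attendance, 30% MD and 105 kg; the documents give neither gap lengths nor mean weight. For % weight change the tipping conclusion will usually be the same under both rules. Individual imputed values, 5% responder status and the responder tipping point can differ.

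A reader might infer that the primary result is in doubt. It is not: the jump-to-reference analysis uses no weights between baseline and week 56, and the sample size does not use this rule. Only the weight-regain and tipping-point sensitivity analyses are affected.

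**What to change.** In SAP Table 2–5 and protocol Table 17–5, change the start of the month count from drop-out to the LAO. Do this in the regain row (the liraglutide rule and part (a) for placebo) and in the tipping-point row. In the same rows, state that an LAO above baseline is carried forward unchanged, as SAP 2.3.2.2 already says; changing the clock alone would leave that second mismatch.

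The cost is table wording in two documents. No new data are needed, and the primary analysis, test hierarchy and sample size do not change.

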17.3.4 Subgroup analyses for primary endpoints

For the primary estimand, subgroup analyses will be done for the factors listed and categorised as in [Table 17-4](#). For baseline weight, categories based on quartiles will be used. The subgroup analyses will be done separately for each of these by including interaction term(s) with randomised treatment arm in the respective models (ANCOVA or logistic regression).

Figure 17–1 Illustration of imputation approaches for the effectiveness estimand

[figure not shown]

Table 17–5 Overview of handling of missing values

| Approach | Description | Assumptions |
|---|--|---|
| Jump to reference (multiple imputation) | Liraglutide and placebo MT+MD imputed from placebo AT+AD (i.e., all available placebo assessments at week 56) | - Liraglutide MD lose any treatment effect instantly after drop-out - Placebo AT and placebo AD are assumed to have the same weight loss |
| McEvoy (multiple imputation) | Separately for the two randomised treatment arms: MD imputed from AD by matching on time (month) of drop-out MT imputed from AT | - AD is representative of the MD for each randomised treatment arm - AT is representative of the MT for each randomised treatment arm |
| Weighted ANCOVA (wANCOVA) | No imputation. Separately for the two randomised treatment arms: AD subjects are up-weighted relative to their proportion of AD+MD and timing of drop-out AT subjects are up-weighted relative to their proportion of AT+MT | - AD is representative of the MD for each randomised treatment arm - AT is representative of the MT for each randomised treatment arm |
| Sacks (single imputation) | Liraglutide MD imputed by minimum of LAO+0.3 kg and baseline value for each month from drop-out to week 56 and either a) Placebo MD imputed by minimum of LAO+0.3 kg and baseline value for each month from drop-out to week 56 or b) MT (both randomised treatment arms) and placebo MD are imputed by LAO | a) Liraglutide and placebo MD lose any treatment effect linearly after drop-out. b) Only liraglutide MD lose any treatment effect linearly after drop-out. No change in treatment effect since LAO for others. |

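### The overview tables reset a drop-out's observed weight gain to baseline in the 0.3 kg/month regain and tipping-point analyses, while the text carries that gain forward

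*SAP*

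**What the plan says.** The text under the sensitivity analyses in SAP 2.3.2.2 has two parts for MD subjects. Regain is added to the LAO and capped: "Change from baseline is truncated whenever the extrapolation would lead to a positive weight gain relative to baseline". If the LAO is itself above baseline, "no additional gain will be imputed, and the unfavourable gain is carried forward to week 56". The tipping-point paragraph takes over these rules by reference: "In a similar manner as above for a range of weight regain rates", applied to liraglutide MD only. Protocol 17.3.2.2 has the same text, and Amendment 1 does not change it.

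The tables give one formula with no exception for an LAO above baseline:

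- Regain row, liraglutide (Protocol Table 17-5; same in SAP Table 2-5): "Liraglutide MD imputed by minimum of LAO+0.3 kg and baseline value for each month from drop-out to week 56".
- Regain row, version (a), placebo: "a) Placebo MD imputed by minimum of LAO+0.3 kg and baseline value for each month from drop-out to week 56".
- Tipping-point row, liraglutide: "Liraglutide MD imputed by minimum of LAO+X kg (X in steps of 0.1) and baseline value for each month from drop-out to week 56".
- Version (b) and tipping point, all others: "MT (both randomised treatment arms) and placebo MD are imputed by LAO". MT are subjects on treatment whose week 56 value is missing.

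The SAP says that Figure 2-1 and Table 2-5 "give an overview of the handling of missing values at week 56" assessments. It does not say whether text or table prevails.

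**The concern.** The tables hold the only closed formula, so they are what a programmer might code. Coded as written, the formula discards an observed unfavourable weight and puts a more favourable one in its place.

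In version (b) and the tipping point this happens in one arm only, because placebo MD and all MT subjects are carried forward without a cap. Both analyses exist to test whether the result survives unfavourable assumptions about liraglutide drop-outs. Under the table rule, the first steps of the tipping point can leave those drop-outs with a better mean than plain LAO would. The text rule never imputes a value below the LAO, so this cannot occur. If the conflict is left open, the choice between the rules could be made once the results are known.

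**Working it through.** **Inputs from the documents.** The two rules as quoted; rate 0.3 kg/month, or steps of 0.1 kg/month for the tipping point; completers -9% vs -4%, SD 7, 141 per arm, 30% discontinuation with none returning (SAP 2.1).

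**Inputs assumed.** The documents give neither LAO values nor an MD share. LAO % change is taken as X ~ N(mu, s), with mu from -2 to -5 and s from 4 to 7. MD share is 15%, or 30% as the planning worst case. Baseline weight is 100 kg, so 0.3 kg is 0.3 points.

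**Plan's own figure.** None exists for this rule. The borrowed planning inputs do reproduce: difference 0.7 x (-5) = -3.5; mixture SD sqrt(49 + 0.7 x 0.3 x 25) = 7.37; power 98.28% against the stated 98.3%.

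**1. The rules on single cases** (baseline 100 kg, 6 months missing, 0.3 kg/month)

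| LAO (kg) | Table rule | Text rule |
|---|---|---|
| 95 | 96.8 | 96.8 |
| 99.5 | 100 | 100 |
| 101 | 100 | 101 |
| 103 | 100 (0%) | 103 (+3%) |

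The rules agree at or below baseline. Above it they differ by the full gain, whatever the rate.

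**2. Mean gap.** With T the total regain in points, the text rule is max(X, min(X+T, 0)) = min(X+T, 0) + max(X, 0). So text minus table is e(mu, s) = E[max(X, 0)] = s·phi(mu/s) + mu·Phi(mu/s), for every T.

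- mu = -4, s = 7: P(X > 0) = 28.4%, e = 1.237.
- Smallest on the grid (mu = -5, s = 4): P = 10.6%, e = 0.202.
- Largest (mu = -2, s = 7): P = 38.8%, e = 1.906.

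**3. Effect on the liraglutide mean in version (b) and the tipping point** (MD share x e, unadjusted). At 15% MD: 0.15 x 0.202 = 0.03 to 0.15 x 1.906 = 0.29. At 30% MD: 0.06 to 0.57. For mu = -4, s = 7: 0.19 and 0.37. All shifts favour liraglutide.

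**4. Comparison with plain LAO.** The table-rule mean is (mu+T) - e(mu+T, s); the text rule adds e(mu, s). For mu = -4, s = 7 and six months of regain:

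| kg/month | T | Table | Text | Plain LAO |
|---|---|---|---|---|
| 0.1 | 0.6 | -4.82 | -3.58 | -4.00 |
| 0.2 | 1.2 | -4.41 | -3.18 | -4.00 |
| 0.3 | 1.8 | -4.03 | -2.79 | -4.00 |
| 0.6 | 3.6 | -3.00 | -1.76 | -4.00 |

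In this example the first three steps impose no penalty under the table rule. Break-even is T = 1.85 points, or 1.85 / 0.3 = 6.2 months at 0.3 kg/month. Across the grid it runs from 0.23 to 3.76 points (0.8 to 12.5 months).

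**5. Version (a).** Both arms are reset, so the net effect is MD share x (e placebo - e liraglutide). It is zero if the arms have the same LAO distribution and MD share. With placebo mu = -2 and liraglutide mu = -4 (s = 7), it is 0.15 x (1.906 - 1.237) = 0.10, or 0.20 at 30% MD. In that case the reset narrows the difference, against liraglutide.

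**6. Other endpoints.** A subject at or above baseline is a non-responder at 5%, 10% and 15% under either rule, so test orders 2 to 4 do not change.

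**7. The cap, a separate matter.** Text and tables both stop regain at baseline, so a tipping point may not exist. With 30% MD, none returning, and an unadjusted test, superiority survives any rate in about 78-93% of trials under the table rule and 49-92% under the text rule. The 49% pairs liraglutide LAO -2 with placebo LAO -4; equal means with SD 7 give 60% (-4) or 74% (-2). At 15% MD it is at least 97% under either rule.

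**The case against.** The strongest reply is that the text settles the case. It names the subject whose LAO is a gain and says what to do. The tables are introduced as an overview, and their assumptions column speaks of treatment effect being lost after drop-out, which suggests that the formula was written for weight still to be regained. On this view the point is editorial. It stands in part: the text is the fuller rule and should be taken as the intended one. But no precedence is stated, the tables give the only formula, and the same conflict appears in both documents.

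Other replies also carry weight:

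- For the tipping point, the carry-forward rule applies only by reference, so that conflict is less explicit than for the 0.3 kg/month analysis.
- SAP 3.1 lists departures from the protocol. Since both documents say the same here, its silence shows only that the conflict was not noticed.
- The size is assumed throughout. SAP 2.1 expects liraglutide discontinuers to fall between -4% and -9%. That concerns weight change in general rather than LAO, and early drop-outs may have lost less, but means of -4 to -9 with SD 7 give 10-28% of MD above baseline and shifts of 0.05-0.19 points at 15% MD (0.10-0.37 at 30%). The upper value of 0.57 needs mean -2, SD 7 and 30% MD.
- Protocol 8.1 asks sites to obtain week 56 weights from discontinuers, so 30% MD is a worst case.

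These replies limit the size and the tone. They do not remove the contradiction or its one-sided direction.

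**Conclusion.** The contradiction holds as written and needs no assumption: for an LAO above baseline, the tables impute 0% change and the text imputes the observed gain. It is explicit for the 0.3 kg/month analysis and by reference for the tipping point.

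Its reach is narrow: MD subjects above baseline, continuous % weight change, and sensitivity analyses only. The primary jump-to-reference analysis, the testing hierarchy and the sample size are untouched.

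The shift is modest beside -3.5 and illustrative, since it rests on an assumed normal LAO distribution and an assumed MD share. What justifies correcting it is the direction: in version (b) and the tipping point, the table rule drops unfavourable data from the liraglutide arm alone.

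Two further points are missing detail, not errors. The SAP does not say what is reported if superiority survives at the baseline cap. SAP Table 2-6 lists a tipping point for test orders 6 to 9, but the only step defined is in kg.

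**What to change.** In the regain and tipping-point rows of SAP Table 2-5, replace the formula with max(LAO, min(LAO + rate x months, baseline)). This reproduces the existing text exactly and introduces no new method. An entry in SAP 3.1 can state that it also replaces the formula in Protocol Table 17-5, so no protocol amendment is needed.

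Add two clarifications:

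- For % weight change, if superiority survives at the cap, report that no tipping point was found up to full regain to baseline, with the MD share in each arm. An uncapped version is optional.
- For test orders 6 to 9, state that the tipping-point step is in the endpoint's own units and in the unfavourable direction.

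The cost is one line per table row, a short programming check and two sentences. The primary analysis, sample size and data collection do not change. Version (b) and the tipping point may look slightly less favourable to liraglutide than under the table formula.

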2.4 Section 4.2.2.2 Supportive secondary endpoints

Change from baseline to week 56 in:

- HbA_{1c} (%)
- Fasting plasma glucose (mg/dL)
- *Systolic blood pressure (mmHg)*
- Diastolic blood pressure (mmHg)
- Lipids (total cholesterol [TC], low density lipoprotein cholesterol [LDL cholesterol], high density lipoprotein cholesterol [HDL cholesterol], very low density lipoprotein cholesterol [VLDL cholesterol], triglycerides [TG], free fatty acids [FFA])
- ~~Short Form-36 v2.0 acute (SF-36) (physical component summary (PCS), mental component summary (MCS) and subdomains)~~
- *SF-36 v2.0 acute:*
 - *role-physical score*
 - *bodily pain score*
 - *general health score*
 - *vitality score*
 - *social functioning score*
 - *role-emotional score*
 - *mental health score*
 - *physical component summary (PCS)*
 - *mental component summary (MCS)*

- *IWQoL-Lite for CT*
 - *pain/discomfort domain score*
 - *psychosocial domain score*
 - *total score*
- Weight related sign and symptom (WRSS) measure, total score

~~Proportion of subjects with the following at week 56:~~

Subjects who after 56 weeks achieve (yes/no):

- ≥ 4.3 T-score points increase from baseline in SF-36 physical functioning score
- ≥ 2 3.8 T-score points increase from baseline in SF-36 PCS
- ≥ 3 4.6 T-score points increase from baseline in SF-36 MCS
- Responder definition value for IWQoL-Lite for CT physical function domain (5-items) score

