## Table 2–6Hierarchical order and type of statistical method to address the effectiveness
estimands for primary and confirmatory secondary endpoints

Test order	Endpoint	Endpoint Type	Statistical model	MI approach	Sensitivity analyses #
	Primary endpoints				
1	Change in body weight (%) from baseline to week 56	Continuous	ANCOVA	Jump to reference	McEvoy wANCOVA Sacks Tipping point Unadjusted ANCOVA
2	Proportion of subjects losing at least 5% of baseline body weight at week 56	Binary	Logistic Regression	Jump to reference	McEvoy Sacks Tipping point Risk difference
	Confirmatory secondary endpoints				
3	Proportion of subjects losing more than 10% of baseline body weight at week 56	Binary	Logistic Regression	Jump to reference	McEvoy Tipping point
4	Proportion of subjects losing more than 15% of baseline body weight at week 56	Binary	Logistic Regression	Jump to reference	McEvoy Tipping point
5	Proportion of subjects losing at least 4% of baseline body weight at week 16 (addresses the effectiveness estimand for week 16)	Binary	Logistic Regression	Not needed, as subjects with missing body weight values at week 16 will be considered non-responders.	
6	Change from baseline to week 56 in waist circumference (cm)	Continuous	ANCOVA	Jump to reference	McEvoy wANCOVA Tipping point
7	Change from baseline to week 56 in Short Form-36 (SF-36) v2.0 acute physical functioning score	Continuous	ANCOVA	Jump to reference	McEvoy wANCOVA Tipping point
8	Change from baseline to week 56 in impact of Weight on Quality of Life-Lite (IWQoL-Lite for CT), physical function domain (5-items) score	Continuous	ANCOVA	Jump to reference	McEvoy wANCOVA Tipping point
9	Change in six minute walking distance test (m) from baseline to week 56	Continuous	ANCOVA	Jump to reference	McEvoy wANCOVA Tipping point

MI Multiple Imputation;

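### The only tipping-point rule is written for body weight, and as written it runs the wrong way for SF-36 PF, IWQoL-Lite for CT PF and 6MWT

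*SAP*

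**What the plan says.** SAP section 2.3.2.2 describes the tipping-point analysis "for a range of weight regain rates (starting from 0.1 kg/month and in intervals of 0.1 kg/month) for MD in liraglutide 3.0 mg arm", "used to define a tipping point in which superiority of liraglutide 3.0 mg disappears". It works like the single-imputation regain analysis listed just before it. In that analysis regain stops at baseline, and when the last available observation (LAO) already lies above baseline, "no additional gain will be imputed, and the unfavourable gain is carried forward to week 56".

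The Tipping point row of SAP Table 2–5 (repeated in Protocol Table 17–5) states the rule as "Liraglutide MD imputed by minimum of LAO+X kg (X in steps of 0.1) and baseline value", applied for each month from drop-out to week 56. It adds that "MT (both randomised treatment arms) and placebo MD are imputed by LAO". The Assumptions column of the row says that only liraglutide missing drop-outs (MD) lose their treatment effect, and that they lose it linearly.

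Table 2–6 assigns the analysis to test order 7, "Short Form-36 (SF-36) v2.0 acute physical functioning score Continuous ANCOVA Jump to reference McEvoy wANCOVA Tipping point", to order 8 (IWQoL-Lite for CT physical function) and to order 9, "Change in six minute walking distance test (m) from baseline to week 56". Its footnote points only to Table 2–5. Protocol Amendment 1 makes the same assignments. Neither document gives another sign, unit or step for these endpoints. By contrast, SAP section 2.4.1 does adapt the ANCOVA for secondary endpoints, by swapping the baseline covariate.

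**The concern.** For weight, adding X is deterioration, and the minimum stops the deterioration at baseline. For orders 7–9 the documents show the opposite scale direction. The expected differences in SAP Table 2–3 are positive (+0.9, +3.5, +1.7). Amendment 1 defines SF-36 response as a "4.3 T-score points increase from baseline in SF-36 physical functioning score". Protocol section 8.3.8 asks the subject to walk as far as possible. On such scales, adding X is improvement and the minimum selects the worse of two values. Kilograms also have no meaning for a T-score, a questionnaire score or metres.

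A tipping-point analysis needs a penalty that grows with X until superiority is lost. If the penalty shrinks or becomes a credit, the reported result misstates how far the finding depends on the missing data.

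**Working it through.** **1. Inputs and the plan's own figures.** SAP Table 2–3 gives completer means (liraglutide, placebo) and SD: SF-36 PF 3.7, 2.4, 8; IWQoL-Lite PF 16, 11, 18; 6MWT 8.2, 5.8, 12. With 30% discontinuation, the liraglutide mean is 0.7 × active + 0.3 × placebo. For IWQoL-Lite this is 0.7 × 16 + 0.3 × 11 = 14.5, so the difference is 3.5. The mixture SD is √(18² + 0.21 × 5²) = 18.1. A Satterthwaite t test with 141 per arm and two-sided α = 0.05 gives power 36.7%. The same steps give 15.8% for SF-36 PF and 21.5% for 6MWT. All three match the table.

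**2. Direction, without assumptions.** With m months from LAO to week 56, min(LAO + X·m, baseline) never falls as X rises. The text rule (LAO carried forward if above baseline, otherwise the same minimum) never falls either. When higher is better, neither can penalise drop-outs progressively.

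**3. Two illustrative SF-36 PF drop-outs, baseline 45, m = 6.** The mirrored rule is max(LAO − X·m, baseline) if LAO is above baseline, otherwise LAO.

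| LAO | X | Table rule | Text rule | Mirrored rule |
|---|---|---|---|---|
| 49 (improved) | 0.1 | 45 | 49 | 48.4 |
| 49 (improved) | 1 | 45 | 49 | 45 |
| 42 (declined) | 0.1 | 42.6 | 42.6 | 42 |
| 42 (declined) | 1 | 45 | 45 | 42 |

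Under the table rule the improver loses everything at the first step, whatever X is. Under both written rules the decliner gains as X grows.

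**4. Size for IWQoL-Lite PF.** Assumptions not in the documents: all 30% of liraglutide discontinuers are MD, their LAO change L follows the placebo completers, N(11, 18²), m = 6, and placebo stays at 11. The difference is 0.7 × 16 + 0.3 × (MD mean) − 11 = 0.2 + 0.3 × (MD mean). The MD mean is E[min(L + 6X, 0)] for the table rule. The text rule adds E[max(L, 0)] = 13.98 to that. The mirrored rule is E[max(L − 6X, 0)] + E[min(L, 0)].

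| X per month | Table: MD mean, difference | Text: MD mean, difference | Mirrored: MD mean, difference |
|---|---|---|---|
| 0.1 | −2.82, −0.65 | 11.16, +3.55 | 10.57, +3.37 |
| 1 | −1.67, −0.30 | 12.32, +3.89 | 6.97, +2.29 |
| 5 | −0.07, +0.18 | 13.91, +4.37 | −1.63, −0.29 |

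LAO carried forward gives +3.5. Rounding can move the last digit by one. At X = 0.1 the table, text and mirrored rules give −0.38, +0.98 and +0.80 for SF-36 PF, and −0.74, +1.73 and +1.56 for 6MWT. With 15% MD, IWQoL-Lite at X = 0.1 is +2.18 under the table rule and +4.18 mirrored; the table rule still rises with X.

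**5. Other assumptions.** With LAO like completers of the same arm and m = 6.5, IWQoL-Lite over the same X values moves from about −0.3 to +0.2 (table), about 5.0 to 5.5 (text) and about 4.9 to 0.2 (mirrored). The direction is the same at 3 and 12 months.

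**6. Simulated trials** (42 liraglutide MD, m uniform on 1 to 12 months), among those significant with LAO imputation:

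| Rule | Outcome | SF-36 PF | IWQoL-Lite PF | 6MWT |
|---|---|---|---|---|
| Table | lost at X = 0.1 | 58 of 61 | 160 of 163 | 86 of 88 |
| Table | lost at a later X | 0 | 0 | 0 |
| Text | lost at any X | 0 of 57 | 0 of 165 | 0 of 97 |
| Mirrored | lost at X = 0.1 | 12 of 65 | 12 of 164 | 11 of 104 |
| Mirrored | lost at a later X | 50 of 65 | 148 of 164 | 89 of 104 |

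Some first-step losses under the table rule were regained as X rose (6, 3 and 6 trials).

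**The case against.** The best defence is the row's own Assumptions column. An effect that wears off linearly means, for these scores, a fall from LAO towards baseline. A rule in kilograms cannot be run on a T-score at all, so a programmer must adapt it, and only the mirrored form fits the stated assumption. That stands as evidence of intent, and a reader should not infer that the sponsor means to test in the wrong direction. It does not repair the plan: the Description column says something else, and sign, unit and step remain unwritten.

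A reader might also infer that a true claim on these endpoints would look fragile because superiority tips at the first step. The documents do not support that as a general statement. It follows from the table wording only; under the section 2.3.2.2 wording the error is the opposite, false robustness.

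Nor is the missing-data assessment of these endpoints empty. Table 2–6 also assigns the McEvoy imputation and the weighted ANCOVA to each, and neither depends on scale direction. The 30% MD share is the plan's deliberately conservative sample-size assumption, and the protocol presses discontinuers to return at week 56. The figures illustrate; they do not predict. Finally, the SAP puts effective power at these steps at 7.2%, 2.7% and 0.6%, by a calculation it calls conservative, so a confirmatory claim here is unlikely on its own planning assumptions.

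**Conclusion.** The point holds in a limited form. Followed as written, the tipping-point analysis cannot give an interpretable result for test orders 7–9, whichever of the two wordings is used, and both contradict the row's own assumption. The direction follows from algebra and from the documented scale direction. The numerical sizes rest on the assumed MD share, LAO distribution and timing, and on unadjusted means.

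The effect is confined to one of three sensitivity analyses for three of the seven confirmatory secondary endpoints. The primary endpoints and the hierarchy are untouched. The 10% and 15% responder endpoints derive from weight and keep the right direction. Waist circumference has the right direction but the wrong unit. Failing to reach a tipping point is not in itself peculiar to these endpoints: because of the cap at baseline, none was reached in 83 of 100 simulated trials for weight under the table rule. What is peculiar to them is that the estimate moves the wrong way.

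**What to change.** In SAP Table 2–5 and Protocol Table 17–5, add a rule for test orders 7–9:

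- Liraglutide MD with LAO above baseline: the maximum of (LAO − X per month) and baseline.
- Liraglutide MD with LAO at or below baseline: LAO carried forward.
- X and its step in the endpoint's own unit (T-score points, IWQoL-Lite points or metres per month), fixed before database lock. The step size is the sponsor's choice.

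Keep the minimum form for weight and waist circumference, with cm for waist. Also align the table with section 2.3.2.2 for subjects whose LAO is worse than baseline: for weight, the table returns them to baseline and the text carries the gain forward.

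The cost is a few lines of wording and a change of sign and bound in the program. No new data are needed.
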